In this multicenter retrospective study, the authors analyzed outcome of HCT in 106 patients with ADA-SCID who received a total of 119 transplants. HCT from matched sibling and family donors (MSD, MFD) had significantly better overall survival (OS) (86% and 81%) in comparison to HCT from matched unrelated (66%; $p < 0.05$) and haploidentical donors (43%; $p < 0.0001$). Superior OS was also seen in patients who received unconditioned transplants in comparison to myeloablative procedures (81% vs. 54%; $p < 0.003$) although in unconditioned haploidentical donor HCT, non-engraftment was a major problem. Long term immune recovery showed that regardless of transplant type, overall T cell numbers were similar although a faster rate of T cell recovery was observed following MSD/MFD HCT. Humoral immunity and donor B cell engraftment was achieved in nearly all evaluable surviving patients and was seen even after unconditioned HCT. These data detail for the first time the outcomes of HCT for ADA-SCID and demonstrate that if patients survive HCT, long term cellular and humoral immune recovery is achieved. These outcomes confirm many previous smaller reports on the rates of success and complications for different types of allogeneic HSCT for ADA-deficient SCID.

Thus, while T cell-depleted or unrelated adult donor or cord blood HSCT have become useful treatment modalities for ADA-deficient SCID patients, they are still beset by a number of serious limitations. Because of these limitations, haploidentical or matched unrelated BMT are generally not offered as options for ADA-SCID. The two conventional treatment options are HLA-identical related BMT for those with available matched siblings and ADA enzyme replacement therapy in the form of PEG-ADA for most others.

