5.1 Primary Endpoints

The primary endpoints are:

- Safety: the incidence and severity of serious adverse events (SAEs)
- Efficacy: overall and event-free survival at 12 months, where events are death, reinstitution of PEG-ADA therapy and performance of an allogeneic BMT.

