8.3.1 Primary Efficacy Endpoints

8.3.1.1 Overall Survival at 12 Months

Overall survival will be evaluated using the time in months from transplant to either the subject's death or their last evaluation calculated as:

12*(date of death/last evaluation – date of transplant)/365.25,

or, for HSCT control subjects for whom the dates were not recorded, as:

age in months at death/end of follow-up - age in months at transplant.

The number (%) of subjects who were still alive at 12 months post-transplant will be summarised. For the purpose of this analysis, any subject who withdrew from the study prior to 12 months, who was known to be alive at the last evaluation, will have a status of "unknown". The proportion and exact 95% confidence interval (CI) for survivors at 12 months post-transplant will be calculated for the OTL-101 treated and each of the HSCT control groups along with the difference in proportions (with 95% CI) between the OTL-101 treated and each of the control groups, excluding those with unknown status.

Final Version 4.0 Page 17 of 27

Overall survival in each treatment group will also be presented using a Kaplan-Meier curve for time to death. For the purpose of this analysis, any subject who withdrew from the study prior to 12 months and was known to be alive at the last evaluation will be censored at the date of their last evaluation. If appropriate, the proportion alive at 12 months and the associated 95% confidence interval will be estimated for each treatment group from the Kaplan-Meier curve along with the median survival time (and interquartile range), if they can be estimated from the data.

If there is at least one event in each group, the log-rank test will be used to compare the difference in survival curves between the OTL-101 treated subjects and each of the HSCT control groups.

In addition, a Bayesian analysis will be carried out. The prior distribution for the rate of survivors in each treatment group will be set to Beta(α =1, β =1) (a conservative non-informative prior). The number of survivors in each group (X) will be estimated and the posterior distribution for the rate of survivors in each group will be updated to Beta(α =1 + X, β =1 +N - X), where N is the total number of subjects in the group. Histograms will be presented for the posterior distributions for each treatment group.

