8.3.1.2 Event-free Survival at 12 Months

Event-free survival will be evaluated using the time in months from transplant to either the first event or their last evaluation calculated as:

12*(date of event/last evaluation – date of transplant)/365.25,

or, for HSCT control subjects for whom the dates were not recorded, as:

age in months at death/end of follow-up - age in months at transplant.

For the purpose of this analysis, the events of interest are:

- death:
- reinstitution of PEG-ADA ERT;
- requirement for a second transplant.

Event-free survival will be summarized in the same way as overall survival described in Section 8.3.1.1.

Final Version 4.0 Page 18 of 27

In addition, if there are any events (other than death), the time to each event will be summarized in a similar manner to the overall event-free survival.

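### The Kaplan-Meier summaries of PEG-ADA restart and of second transplant do not treat death as a competing event, so they can overstate how many children had these failures in any group with deaths

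*SAP*

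**What the plan says.** SAP 5.1 defines the primary efficacy endpoint as "overall and event-free survival at 12 months, where events are death, reinstitution of PEG-ADA therapy and performance of an allogeneic BMT". Death is part of the composite, so it does not compete with it.

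SAP 8.3.1.2 gives the composite the overall-survival methods: "Event-free survival will be summarized in the same way as overall survival described in Section 8.3.1.1". Those methods are the proportion with an exact interval, the difference in proportions, Kaplan-Meier with a 12-month estimate if appropriate, a conditional log-rank test and a Bayesian analysis. SAP 8.3.1.1 states: "Overall survival in each treatment group will also be presented using a Kaplan-Meier curve for time to death".

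The component analyses follow in one sentence. It begins "In addition, if there are any events (other than death" and goes on to say that "the time to each event will be summarized in a similar manner to the overall event-free survival". SAP 8.3.2.1 repeats the 12-month methods at 24 months.

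The only censoring rule written for these analyses is that "any subject who withdrew from the study prior to 12 months and was known to be alive at the last evaluation will be censored". Nothing is said about a child who dies before a restart or second transplant, or about how one non-fatal event is treated in the analysis of the other. No competing-risk method is named in SAP section 8.

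**The concern.** A child who has died can no longer restart PEG-ADA or be re-transplanted. A Kaplan-Meier curve for restart alone has to do something with that child. Counting the death as an event would turn the curve back into a composite, so a programmer would most likely censor at death. Kaplan-Meier then treats the dead child as still able to restart later, and one minus the curve estimates the risk in a hypothetical setting without death. It does not estimate the proportion of children who actually restarted.

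The gap grows with mortality. The primary comparator is HSCT without a matched related donor (SAP 8.3), the donor types with the lowest survival in the protocol's background. Readers will take the component figures as rescue rates, and an overstatement present in one group but absent in the other would distort that reading.

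**Working it through.** The plan gives no figure for the component analyses, so there is nothing to reproduce. The check asks how far one minus Kaplan-Meier (deaths censored) lies from the cumulative incidence (death competing).

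**Inputs**
- Background survival, Protocol 2.1.3.1 part e: matched sibling and family donors "had significantly better overall survival (OS) (86% and 81%) in comparison to HCT from matched unrelated" donors at 66% and haploidentical donors at 43%. No time horizon is stated; reading these as 12-month values is an assumption.
- Protocol Table 1, haploidentical: 21 of 42 alive (50% mortality) and 14 of 42 alive with T-cell engraftment. The difference, 7/42 = 16.7%, serves as a rough proxy for non-fatal failure. That use is an assumption.
- OTL-101, Protocol 2.1.6.2: 100% overall and event-free survival in 18 evaluable patients.
- True restart incidences of 20% and 30% are illustrative; the documents give none.

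**Check 1: constant hazards, overall survival S at 12 months**

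Death hazard d = −ln S, so d = 0.4155 for S = 0.66 and d = 0.8440 for S = 0.43. Find the restart hazard r that solves

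r/(r + d) × [1 − exp(−(r + d))] = true incidence.

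The figure shown by one minus Kaplan-Meier is then 1 − exp(−r).

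| Survival | True incidence | r | Shown |
|---|---|---|---|
| 66% | 20% | 0.277 | 24.2% |
| 43% | 20% | 0.341 | 28.9% |
| 66% | 30% | 0.448 | 36.1% |
| 43% | 30% | 0.558 | 42.8% |
| 81% | 20% | 0.250 | 22.1% |
| 86% | 20% | 0.242 | 21.5% |

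**Check 2: incidence fixed at c = 16.7%, mortality before the event m**

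Under constant hazards, the figure shown is 1 − (1 − m − c)^(c/(m + c)). If every death came after the restarts it would be c; if every death came before them it would be c/(1 − m).

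| m | Constant hazards | Range over timing |
|---|---|---|
| 0% | 16.7% | 16.7% |
| 14% | 18.0% | 16.7–19.4% |
| 34% | 20.7% | 16.7–25.3% |
| 50% | 24.0% | 16.7–33.3% |
| 57% | 26.1% | 16.7–38.8% |

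At 34–57% mortality the overstatement is about 4 to 9 points under constant hazards, and 0 to 22 points over the timing bounds. With no deaths it is zero.

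**Check 3: is the comparison of hazards biased?**

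A simulation (4,000 replicates, 20 per group) gave both groups the same restart hazard, 0.275 per year. OTL-101 had no deaths; controls had a death hazard of 0.824 per year, which corresponds to m = 50% and c = 16.7%.

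| Group | Cumulative incidence | One minus Kaplan-Meier |
|---|---|---|
| OTL-101 | 24.1% | 24.1% |
| Controls | 16.6% | 23.9% |

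One minus Kaplan-Meier shows the two groups as equal, which is correct for the hazards. It misstates the proportion of control children who failed: 16.6% did, and 23.9% is shown.

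**The case against.** The strongest reply is that the SAP nowhere says deaths are censored, so the defect in the text is an unspecified rule. That is correct. But a single-event curve for restart leaves no other natural choice, and the remedy is the same either way.

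A reader might infer that the plan biases the comparison in favour of OTL-101. The documents do not support that, for four reasons.
- A log-rank test with deaths censored is a legitimate comparison of cause-specific hazards, and Check 3 shows no spurious contrast when the hazards are equal. The SAP also limits it: "If there is at least one event in each group, the log-rank test will be used". With no failures in OTL-101, as in the data reported in Protocol 2.1.6.2, it would not be run.
- The control mortality used here is from the literature. Haploidentical survival in Table 1 runs from 3 of 13 in London to 14 of 19 at Duke, so the actual cohort could lie anywhere in a wide range.
- For controls without dates, the formula in SAP 8.3.1.2 uses age at death or end of follow-up. Applied to a restart, it could time the event after 12 months and understate control failures, which is the opposite direction.
- The component summaries are conditional and supplementary; they are not listed endpoints.

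A reader might also fault the simple component proportion because children who died count as free of restart. That does not hold. Its complement is the number who restarted divided by all children with known status, which is the quantity wanted.

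Precision is also poor. Appendix H identifies 25 + 10 = 35 controls of all donor types. If the primary subset were 20, an exact 95% interval around 4/20 would run from about 6% to 44%, wider than the distortion. That limits the practical weight of the point, but it is no reason to keep an estimator of the wrong quantity.

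**Conclusion.** The point holds for the component incidence estimates only. The SAP carries Kaplan-Meier over to PEG-ADA restart and second transplant without treating death as competing. If deaths are censored, the proportion who fail is overstated in any group with deaths.

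On the protocol's background survival for unrelated and haploidentical donors, a true 20% would be shown as about 24% or 29%. With related-donor survival of 81–86% it would be about 21% to 22%, and with no deaths it would be exact. These sizes assume constant hazards and 12-month survival values; they illustrate the mechanism and do not predict the result for the GOSH and Duke cohort.

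Overall survival, composite event-free survival and their Bayesian comparisons stand as they are. This is an inexpensive improvement to a supplementary analysis.

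**What to change.** Amend SAP 8.3.1.2, with the same change at 24 months through 8.3.2.1:

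- For each non-fatal component, report the Aalen-Johansen cumulative incidence at 12 and 24 months with a 95% interval per group, with death and the other first failure as competing events.
- Keep Kaplan-Meier for overall survival and composite event-free survival.
- Label any log-rank test on a component as a comparison of cause-specific hazards.
- Keep the simple component proportion, defined as the event occurring before death among subjects with known status.
- For controls without dates, use age at the non-fatal event in place of age at death or end of follow-up.

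The cost is SAP wording and slightly more programming. For the last item, Protocol Appendix H lists time since transplant for a reinitiated PEG-ADA course at Duke. Its GOSH list does not name the timing of a restart, so the team should confirm that the case report form captures it.

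One drawback needs a line in the report: cumulative incidence can look lower in a group whose patients die first, as in Check 3. Show it beside overall survival so that a low rescue rate is not read as a good outcome.

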8.3.2 Secondary Efficacy Endpoints

8.3.2.1 Overall and Event-free Survival at 24 Months

Overall and event-free survival at 24 months will be summarized in the same way as for the analyses at 12 months described in Sections 8.3.1.1 and 8.3.1.2.

8.3.2.2 Use of Immunoglobulin Replacement Therapy

The number (%) of subjects receiving immunoglobulin replacement therapy (IgRT) will be summarised by visit for the OTL-101 treated subjects.

The time to cessation of IgRT will be calculated (in months) as:

12*(stopping date of IgRT – date of transplant) /365.25,

or, for HSCT control subjects for whom the dates were not recorded, as:

age in months when IgRT stopped – age in months at transplant.

Time to cessation of IgRT will be summarised for the OTL-101 treated and HSCT control groups using descriptive statistics and, if appropriate, estimated from a Kaplan-Meier curve in which subjects who are still receiving IgRT will be censored at the time of their last visit.

The number (%) of subjects who have stopped treatment with IgRT at 12, 18 and 24 months without restarting at any subsequent time point will be summarized for the OTL-101 treated and HSCT control groups (data permitting).

In addition, serum immunoglobulin levels (IgG, IgA and IgM) will be measured at each visit for the OTL-101 treated subjects. Levels of IgG, IgA and IgM and changes from baseline will be summarised by visit using descriptive statistics. In addition, plots of the median value and range over time on a logarithmic scale will be produced for each parameter along with individual plots for each subject which will include age-dependent normal ranges provided by the study sites.

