	drawn at months 1, 2, 3, 4, 5, 6, 8, 10, 12, 15, 18, 21, and 24. Any medically-indicated interventions will be made at those visits. Subjects will then be consented for a long-term follow-up study with semi-annual to annual visits and lab draws over the subsequent 13 years.
Study Duration	Each patient will be followed for 24 months. There will be a separate study for long-term follow-up for these patients for years 3-13. The total follow-up period for these subjects will be up to 15 years.
Study Agent/Intervention Description	The Investigational New Drug to be tested is autologous BM CD34+ cells transduced ex vivo with a self-inactivating (SIN) HIV-1 based lentiviral vector: EFS-ADA (also referred to as OTL-101). The vector has been produced as cell-free lentiviral supernatant from the 293T cell line, and has an envelope pseudotype from the vesicular stomatitis virus (VSV). The vector will be used for ex vivo transduction of CD34+ progenitor cells from the BM of infants or children with adenosine deaminase (ADA)-deficient severe combined immunodeficiency (SCID). OTL-101 will be subsequently infused intravenously after a single non-myeloablative dosage of busulfan (4 mg/kg intravenously x1).
Primary Objective	The primary objectives are: 
 to examine the safety of autologous transplantation of bone marrow CD34+ cells transduced with the EFS-ADA lentiviral vector (OTL-101). The safety review will include the identification of grade III/IV serious adverse events (SAE). Subjects will also be monitored for clinical toxicities, replication competent lentivirus, and monoclonal expansion at regular intervals by a clinician, as well as standard blood counts and chemistries. to estimate overall and event-free survival by 12 months where failure is defined by one of the following endpoints: death; reinstitution of PEG-ADA; or performance of an allogeneic BMT.

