17.8 Appendix H: Details of historical HSCT control groups

1. Objective

Historical data from ADA-SCID patients who were treated with Hematopoietic Stem Cell Transplantation (HSCT) at GOSH/UCL (UK) or Duke University Children's Hospital (USA) during the period of 2000-2016 will be collected. HSCT currently corresponds to the standard of care for ADA-SCID patients. These data will be used as historical control groups in a current on-going gene therapy study "*Phase I/II, controlled, open-label, non-randomised, single-centre trial to assess the safety and efficacy of EF1 α S-ADA lentiviral vector mediated gene modification of autologous CD34+ cells from ADA-deficient individuals*". The objective is to compare gene therapy versus HSCT to determine the optimal treatment.

2. Study populations

The control groups will be constituted of patients of 0 to 18 years of age with a confirmed diagnosis of ADA deficiency, transplanted at Great Ormond Street Hospital (UK) or Duke University Children's Hospital (USA) between 2000 and 2016. See inclusion criteria page 64.

3. Data to be collected – GOSH/UCL

GOSH hold a registry / clinical database (European Society for Immunodeficiencies – ESID and European Bone Marrow Transplant Registry - EBMT) displaying information on patients who have received HSCTs. 25 treated patients have been identified between 2000-2016. The patients have given consent for their data to be entered into this registry / clinical database and to be used for other ethically approved studies. ESID and EBMT will allow us to collect the below information:

- Demographics (gender, date of birth, date of death),
- Date of treatment with HSCT
- Method of ADA-SCID diagnosis,
- Previous HSCT including: date, transplant cells, donor type and outcome and whether they needed a second transplant.

However, to make this historical control group valid for marketing authorisation application, our discussions with regulatory agencies suggests that we need to collect further information valuable to compare the efficacy and safety of any new treatment in research vs. current HSCT standard of care as:

- Previous PEG-ADA ERT (and duration of treatment),
- Previous or current immunoglobulin therapy,
- Listing of relevant medical history, including infections (severe or opportunistic infections)
- Vaccination
- Auto-immune disease
- Oncology disease / leukemia
- AEs and SAEs

- Death and reason for death

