5.2 Secondary Endpoints

Secondary endpoints for this study are:

- Overall survival and event-free survival at 24 months
- Efficacy of gene transfer/engraftment of HSC
- ADA expression: enzyme activity and detoxification

Final Version 4.0 Page 10 of 27

- Effects on ADA reconstitution on immune phenotype and function (the need for IgRT will be assessed under this category)
- Immune reconstitution
- Infection rates

6 Timing of Analyses

The statistical analyses of data from this study will be performed in three stages:

Interim look:

- Performed after all subjects have completed 6 months of follow-up post infusion
- Descriptive statistics for all available data
- Comparisons between OTL-101 treated subjects and HSCT control cohorts of demographics and overall survival

Primary analysis:

- Performed after all subjects have completed 12 months of follow-up post infusion
- Descriptive statistics for all available data
- Comparison to HSCT control cohorts on overall and event-free survival (primary efficacy endpoints), use of immunoglobulin replacement therapy (IgRT) and infection rate (key secondary endpoints).

End of study analysis:

- Performed after all subjects have completed the study (24 months of follow-up post infusion)
- Descriptive statistics for the complete study cohort
- Comparison to HSCT control cohorts on overall and event-free survival (primary efficacy endpoints), use of immunoglobulin replacement therapy (IgRT) and infection rate (key secondary endpoints).

7 Analysis Populations

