7.2 Safety Population

The safety population will consist of all subjects treated with OTL-101 at UCLA/NIH (current study cohort) and the complete HSCT historical control cohort consisting of ADA-SCID patients with any type of donor treated with HSCT at either GOSH or Duke University from the year 2000 onwards.

8 Statistical Methods

In general, continuous variables will be summarised using the mean, standard deviation, median, minimum, maximum and number of subjects. Categorical variables will be summarised using number of subjects and percentages.

For all summaries, the HSCT controls will be summarised in the groups of those without a matched related donor, those with a matched related donor and all subjects.

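### Time to IgRT cessation: the only between-group time summary the SAP guarantees uses stoppers alone, with no common follow-up horizon

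*SAP*

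**What the plan says.** The endpoint matters to the comparison with HSCT. SAP section 6 (Timing of Analyses) lists, for both the primary and the end-of-study analysis, "use of immunoglobulin replacement therapy (IgRT) and infection rate (key secondary endpoints".

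SAP 8.3.2.2 then does three things:

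- It defines the time as "12*(stopping date of IgRT – date of transplant) /365.25", or as a difference in ages for controls without dates. It summarises that time in both groups: "Time to cessation of IgRT will be summarised for the OTL-101 treated and HSCT control groups using descriptive statistics and, if appropriate". The opening of SAP section 8 says what such a summary contains: "continuous variables will be summarised using the mean, standard deviation, median, minimum, maximum and number of subjects".
- The same sentence goes on to a time "estimated from a Kaplan-Meier curve in which subjects who are still receiving IgRT will be censored at the time of their last visit". The conditional wording applies to this part, and no criterion for it is given.
- The next paragraph adds "The number (%) of subjects who have stopped treatment with IgRT at 12, 18 and 24 months without restarting at any subsequent time point", for both groups, subject to data availability.

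None of the three is named as the main comparison, and no test of cessation time is planned. Deaths on IgRT are not addressed.

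On follow-up, the Protocol Summary says of OTL-101: "Each patient will be followed for 24 months". Protocol Appendix H describes controls "transplanted at Great Ormond Street Hospital (UK) or Duke University Children's Hospital (USA) between 2000 and 2016". SAP 8.2.17 takes control follow-up from the eCRF without a cap, and Protocol 11.2 commits every analysis to all relevant available data.

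**The concern.** A child still on IgRT has no stopping date and so no value to enter in a mean or median. The descriptive summary therefore conditions on having stopped within the observed follow-up. It tells us how quickly the stoppers stopped in the time available, not how soon treated children come off IgRT.

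That would be tolerable if both groups were observed for the same time, but the plan does not ensure this. An OTL-101 stop can be recorded only up to 24 months, whereas a control transplanted in the early 2000s could contribute a stop many years out. Late stops lengthen the control mean and cannot lengthen the OTL-101 mean. At the primary analysis the OTL-101 window is shorter still, since SAP section 6 guarantees only 12 months.

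The survival section is firmer: SAP 8.3.1.1 presents the Kaplan-Meier curve without condition and states when the log-rank test is used. For IgRT, the method that handles incomplete follow-up is optional and the one that does not is fixed. At stake is a raw between-group difference in months, on a key secondary endpoint, that can arise with no treatment difference.

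**Working it through.** The documents give no expected cessation time, power or sample size for this endpoint, so there is no figure of theirs to reproduce. The check asks what the stoppers-only summary shows when cessation times have the same distribution in both groups.

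**Inputs from the documents.** OTL-101: n = 20, followed 24 months. HSCT: 25 children from GOSH plus 10 from Duke = 35 (Protocol Appendix H). The primary comparator, those without a matched related donor, is a subset whose size is not stated.

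**Assumptions.** Exponential time to cessation, true median 6, 12, 18 or 24 months. Control follow-up of 24 months, uniform 24-60, or uniform 24-192 (192 = 16 years, the span 2000-2016). Never-stoppers 0% or 20%. Control deaths in the first 12 months 0% or 30%, independent of cessation. 1,500 simulated trials per scenario.

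**Closed form.** With rate λ = ln 2 / median and follow-up c, the mean among stoppers is

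E[T | T ≤ c] = 1/λ − c·e^(−λc) / (1 − e^(−λc)).

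For a true median of 12 months, 1/λ = 17.3.

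- c = 24: e^(−λc) = 0.25, so 17.3 − 24 × 0.25/0.75 = 17.3 − 8.0 = 9.3 months.
- c = 60: e^(−λc) = 0.031, so 17.3 − 60 × 0.031/0.969 = 17.3 − 1.9 = 15.4 months.

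The true distribution is the same; only the observation window differs.

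**Simulated stoppers-only means in months, OTL-101 v HSCT (no deaths, no never-stoppers).** In brackets, the share of trials in which the OTL-101 stoppers-only median is the lower; about 50% means no bias.

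| True median | Controls 24 | Controls 24-60 | Controls 24-192 |
|---|---|---|---|
| 6 | 7.0 v 7.1 (51%) | 7.1 v 8.2 (56%) | 7.0 v 8.5 (60%) |
| 12 | 9.3 v 9.3 (52%) | 9.3 v 13.2 (73%) | 9.3 v 16.3 (84%) |
| 18 | 10.1 v 10.2 (51%) | 10.1 v 15.6 (79%) | 10.2 v 22.6 (93%) |
| 24 | 10.6 v 10.7 (51%) | 10.5 v 17.1 (83%) | 10.6 v 28.0 (97%) |

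Differences of about 0.1 month are simulation noise. At a true median of 12, the stoppers-only medians are 8.3 v 10.5 (24-60) and 8.3 v 12.0 (24-192), so the median is affected less than the mean.

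**Source of the gap.** With 20% never-stoppers, true median 12 and controls at 24-192 months, the means are 9.3 v 16.1, against 9.3 v 16.3 with none. Unequal follow-up drives the gap; permanent non-stoppers hardly change it.

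**Effect of early control deaths (30%).** At true median 12 and 24-192 months, the gap shrinks to 9.4 v 14.8. At true median 6 and 24-192 months, the OTL-101 median is lower in only 43% of trials. At equal 24-month follow-up and true median 12, the means are 9.4 v 8.4, now favouring HSCT.

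**After the fix.** The Kaplan-Meier proportion stopped by 24 months is the same in both groups: 94%, 75%, 60% and 50% for true medians of 6, 12, 18 and 24 months, and within one point of that with 30% control deaths. Cutting control times at 24 months also equalises the stoppers-only mean when nobody dies early (9.3 v 9.3 at true median 12), but not with 30% early control deaths.

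**The case against.** A reader might infer that children who never stop disappear from this endpoint and that the plan is bound to favour OTL-101. The documents do not support either inference.

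- The sentence that fixes the descriptive summary also plans a curve that censors children still on IgRT, and the next paragraph counts stops at 12, 18 and 24 months over subjects. Section 8 requires the number of subjects with each summary, so the number of stoppers will be visible.
- Long control follow-up is inferred from the transplant years and the missing cap. Appendix H frames survival at 1 and 2 years, and its last Duke laboratory window is 17-30 months. Neither limits the IgRT data, but shorter control follow-up is plausible. A separate check with lognormal times, no deaths and controls followed 18-30 months gave mean gaps of only −0.1 to +0.3 months.
- Direction depends on deaths. The protocol's multicentre transplant review (2.1.3.1) quotes survival of 66% with matched unrelated and 43% with haploidentical donors, the kind of donor relevant to the primary comparator. Early deaths remove slow stoppers from the control summary and can reverse the gap.
- Protocol 2.1.6.2 reports that all UCLA patients with sufficient follow-up had stopped IgRT. It gives no times, but fast cessation would keep the artefact small.

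All of this stands, and it limits the size and direction that can be claimed. It does not make the raw comparison interpretable. The curve may be omitted at discretion, the fixed-time counts depend on data availability, and a displayed n does not correct a mean. The fixed-time counts also require no later restart, which gives longer-followed controls more time to fail that condition.

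**Conclusion.** The point holds in a limited form. The only between-group time summary that the SAP makes unconditional is restricted to stoppers and has no common horizon, so its mean and median are not comparable between OTL-101 and HSCT unless follow-up happens to match.

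With no true difference, no deaths and a true median of 12 months, the spurious advantage to OTL-101 in the mean is about 4 months (13.2 − 9.3 = 3.9) with controls followed 24-60 months, and about 7 months (16.3 − 9.3 = 7.0) with 24-192 months. At a true median of 6 months it is 1.1 to 1.5 months. These figures rest on assumed exponential cessation and assumed control follow-up. The documents state neither, and the sign is not fixed once early control deaths are allowed.

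Because IgRT use is a key secondary comparison and the remedy is already half written, the SAP should be changed. The survival analyses are unaffected.

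**What to change.** In SAP 8.3.2.2:

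1. Delete the *if appropriate* condition. Make a time-to-event estimate over all treated children the required between-group summary, with every group cut at 24 months. Report the proportion stopped by 12, 18 and 24 months with 95% confidence intervals, and the median if it is reached.
2. State how death on IgRT is treated. Either Kaplan-Meier with censoring at death or cumulative incidence with death as a competing event would serve, but they answer different questions and the SAP should name one.
3. Drop the raw between-group statistics of cessation time. If they are kept, limit them to stops by 24 months in every group, label them as stoppers only, and print n stopped / n treated beside them. At the primary analysis, where only 12 months of OTL-101 follow-up is guaranteed, the limit for a raw summary would need to be 12 months. Even so limited, the raw summary remains open to distortion by early control deaths, which is why dropping it is cleaner.

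The cost is SAP wording: the dates or ages and the curve are already planned. The price is that control cessation times beyond 24 months no longer enter the between-group comparison. They can still be described for the controls alone.
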